7.2 Study Timeline

Year		1				2				3				4	
Quarter		1	2	3	4	1	2	3	4	1	2	3	4	1	2
Project- months	Pre-grant start	3	6	9	12	15	18	21	24	27	30	33	36	39	42
Trial Stage	Using Enabling Grant Award	Set	up		Recruit	ment and Follow-up			Follow-up				Analysis and Reporting		
Pilot study with implantation of 4 OriLens devices	x X														
Identification of six potential sites	x														
Protocol Development and finalising of Trial Manual after trial of four participants	×														
Training Pack development and collation including surgical movie	×														
R&D Approvals		Х	Х												
Site Training		Х	Х	Х											
Main Study					Х	Х	Х	Х	Х						
Number of sites open			5	8	10	10	10	10	10	10	10	10	10		
Participant Recruitment				10	20	40	80	120	132						
Participant Follow up				Х	Х	Х	Х	Х	Х	Х	Х	Х	Х		
Interim Analysis							Х								
stop & go POINT (safety)							Х								
Data Collection (including HRQoL)			Х	Х	Х	Х	Х	Х	Х	Х	Х	Х	Х		
Management Meetings		XXX	XXX	XXX	XXX	XXX	XXX	XXX	XXX	XXX	XXX	XXX	XXX	XXX	XXX
DMEC		Х		Х			Х		Х				Х		Х
TSC		Х		Х			Х		Х				Х		Х
Trial Close Down (sites)														Х	Х
Data Analysis														Х	Х
Health Economics Analysis														Х	Х
Trial Report														Х	Х
Dissemination															Х

Table 1: MIRROR STUDY TIMELINE

7.3 **Project Milestones**

The duration of the study will be 42 months. A maximum of 10 centres will be required for the study with each site recruiting approximately 13-14 participants. As training will be required in participant selection, visual function testing, surgical implantation, and the use of the telescope, the study investigators would prefer to open eight sites only. However, if recruitment is not progressing to target, consideration will be given to opening new sites. The first six months will be spent on study setup, recruitment of staff, and in the initiation of surgical and low vision training of staff at all sites. A period of 18 months has been allocated for the recruitment phase (months seven to 24). Twelve months follow-up will be required after recruitment of the last subject and six months for analysis of data and dissemination of results including report writing and submission of papers. Project recruitment will be measured to determine that the target sample of 132 is achievable with the number of recruiting sites indicated.

8 Methods: participants, interventions, and outcomes

8.1 Study Setting

Participants will be recruited from a maximum of 10 NHS/Foundation Trusts with retinal specialist clinics across the UK. A list of study sites will be maintained in the TMF and can be obtained from the NICTU.

8.2 Eligibility Criteria

8.2.1 Selection of Subjects

Individuals with bilateral stable advanced AMD (neovascular or atrophic) who have had uncomplicated bilateral cataract surgery with visual acuity of 6/38-6/240 (LogMAR 0.80 to 1.60) will be screened according to the protocol.

8.2.2 Inclusion Criteria

- Age 55 years or above
- Bilateral stable advanced AMD either neovascular (required to be stable for at least 12 months after last treatment) or atrophic AMD
- Bilateral uncomplicated cataract surgery with unifocal intraocular lenses
- Bilateral BCDVA of 6/38- 6/240 (LogMAR 0.80 to 1.60) and above
- Must demonstrate a 10-letter (0.20 LogMAR) improvement in BCDVA (ETDRS chart) with the external x2.5 telescope in the eye for implantation
- Must have had experience of using low vision aids
- Have an endothelial cell density appropriate for age as detailed in Appendix I
- Be willing to undergo laser capsulotomy in the eligible eye prior to randomisation (if required)
- Must be three months or more following any intraocular surgical or laser procedure
- Must be in good general health with every likelihood of involvement in the trial for the duration of the study and be able to physically or verbally complete the questionnaires
- Only one eye per participant will be included in the study.

8.2.3 Exclusion Criteria

- Cataract surgery with multifocal intraocular lenses
- A history of glaucoma or of being on anti-glaucomatous medication
- Any other retinal condition
- Lack of clear view of the retina
- Abnormal or de-centred pupil
- Endothelial cell density <1500 cells/mm²
- History of ocular inflammatory disease
- Zonular instability or instability of existing intraocular lens
- BCDVA of better than 6/38 (0.80 LogMAR) or worse than 6/240 (1.60 LogMAR) in either eye
- Participants unable to provide informed consent
- Be in poor general health that could compromise attending follow-up assessments
- Difficulties with balance
- Not fluent in English*

* Fluency in English is required due to the complexity of screening examinations (reading speed is tested), the detailed explanations given for examinations and interventions, and the type of rehabilitation required.

8.2.4 Selection of Study Eye

As there is little evidence to indicate whether implantation should be in the dominant or nondominant eye, eye selection will be based on the eye achieving the best visual acuity. Ocular dominance will be recorded and analysed as an independent factor but will not be used as a parameter in eye selection unless, as indicated below, the visual acuity with the external simulator is equal in both eyes. The overriding important factor in eye selection is that the eye selected for study should have better distance acuity with the external simulator than the non-study eye with best spectacle correction, otherwise the device is likely to be ignored/suppressed. If the visual acuity is equal in both eyes, then the device will be implanted in the non-dominant eye. The study eye will be proposed by the Eye Selection Committee and confirmed by the manufacturer prior to randomisation. Manufacturer advisement on eye selection is standard clinical practice.

8.2.5 Co-enrolment guidelines

Participants currently enrolled in any other study, which involves the delivery of any investigational medicinal product (IMP) or device intraocularly, will be excluded. Participants currently enrolled in any observational study are potentially eligible for co-enrollment in the current study. This will be decided on a case by case basis by the PI. The CTU should be informed if co-enrollment is being considered and it should be documented in the CRF.

8.2.6 Trial Site requirements

The trial will take place in a maximum of 10 NHS/Foundation Trusts with retinal specialist clinics across the UK. Preference will be given to those sites with experience in the delivery of ophthalmology clinical trials and access to this patient population with sufficient infrastructure support to screen, recruit, consent and randomise participants. The study requires that sites have access to the following equipment and services:

- ETDRS Visual acuity charts and illuminated box
- Reading acuity and reading speed tests (Pelli Robson CS test, Bailey Lovie word reading charts and MN Read reading charts)
- Standard equipment for refraction
- Standard equipment for orthoptic examination
- Slit lamp
- Colour fundus camera with FFA capability
- Optical Coherence Tomography
- Endothelial cell analyser (contact or non-contact)
- Low Vision Service providing low vision aids suitable for distant and near vision tasks

Preference will be given to sites which also have:

• Microperimeter

Equipment which will be provided:

- External x2.5 telescope
- MARS chart for contrast sensitivity (The Mars Perceptrix Corporation)

8.2.7 Research Team Requirements

Staff must demonstrate and document a willingness to comply with the protocol, SOPs, trial specific procedures, the principles of International Conference on Harmonisation (ICH)-Good Clinical Practice (GCP) and regulatory requirements and be prepared to participate in locally-delivered trial-specific training. In particular, the site must have access to the following team members:

- Research nurses
- Research accredited optometrists
- Ophthalmic imaging technicians
- Orthoptist
- Additional masked assessor for BCDVA at 12 month follow-up

8.3 Interventions

The planned interventions will be posterior Nd:YAG capsulotomy in the study eye (if not already done) for all eligible participants followed by: Group 1- implantation of the OriLens device plus three sessions of low vision training; Group 2- three sessions of low vision training. In order to minimise the possibility of a placebo effect an equal number of low vision sessions will be given in each Group.

8.3.1 Intervention description

Group 1: Intervention

The implantation of the OriLens device will be carried out as a secondary surgical procedure no more than eight weeks post randomisation. Participating surgeons will be trained in the surgical procedure for implantation at the beginning of the trial: an instructional video developed by the research team will be available and the CI may observe the first procedure at each site at the request of the PI. The degree of difficulty of this intervention is considered to be small for experienced cataract surgeons. The pupil will be dilated. Local anaesthetic will be used according to the individual surgeon's preference. A minimal incision of 5.5 millimetres is recommended. The wound can either be a scleral flap or tunnel according to the surgeon's preference. The anterior chamber will be filled with viscoelastic and the implant will also be covered in viscoelastic material before insertion. It is important that the optic does not come into contact with the forceps. The orientation of the device should be checked: the lens should vault backwards and the end of the superior haptic should point to the right. Both loops of the device are to be placed in the sulcus. Implantation should not proceed if there is evidence of zonular or existing intraocular lens instability. All viscoelastic will be removed at the end of the surgery. Closure of the incision will be according to surgeon's preference. A peripheral iridotomy is not a routine requirement but may be carried out at the surgeon's discretion. An intracameral injection of antibiotics and a subconjunctival injection of steroids will be administered according to the surgeon's preference. Post-operative management is similar to phacoemulsification surgery and is according to the surgeon's preference. Participants will be prescribed combined steroid/antibiotic drops for use four weeks post-operatively. A standard surgical report documenting the details above will be completed post-operatively.

If the pupil is <2.5 mm in diameter, small sphincterotomies should be performed at the time of implantation of the device. Recording of concomitant medications during medical history is required to determine presence of such which may have an effect on pupil size.

Refraction, spectacle prescription and provision and three 45 minute sessions of low vision training as per the trial manual will follow post-operatively as per section 10.2.

Group 2: Control

Participants will receive refraction, spectacle prescription and low vision aid provision and three 45 minute sessions of low vision training as per the trial manual.

8.3.2 Intervention adherence

Participants will be required to attend the low vision training sessions in order to adapt to the device. Adherence will be monitored by attendance at all low vision training sessions for both groups.

8.3.3 Intervention discontinuation

Implantation of the OriLens device may not proceed if the participant has zonular instability or for any other reasons deemed appropriate by the surgeon. This will be at the surgeon's discretion.

The OriLens may be removed if required post-operatively. Removal of the OriLens is at the surgeon's discretion and may be requested by the participant.

8.4 Outcomes

8.4.1 Primary Outcome

The primary outcome is change in BCDVA at 12 months after randomisation using number of letters improvement on ETDRS as measured by a masked independent assessor. Visual acuity will be assessed as indicated in the Trial Manual. BCDVA can be a variable endpoint depending on the assessor. In order to reduce variability, participants can be encouraged to read to achieve their best visual acuity. BCDVA at the 12 month time point will initially be measured by the optometrist on the research team. An independent assessor will then repeat the BCDVA at the 12-month time point and this measurement will be used for the primary analysis. Refraction will be carried out by the optometrist on the research team prior to the independent assessment and the independent assessor will be instructed not to look directly into the participant's eyes. As an additional measure, the trial frames will be placed on the participant by the research optometrist, which will aid masking.

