8.5 Participant Timeline

Eligibility will be determined at the screening visits. Surgery in Group 1 will take place at Day 0 with surgical review on days one and seven and study visits for both Groups at months one, three, six and 12. As the presence of the device is obvious to the casual observer, it will not be possible to mask assessors. Participants can also not be masked to the intervention. However, the final BCDVA measurement at 12 months will be duplicated by an additional observer independent to the trial and this measurement will be used for the primary analysis. BCDVA (primary outcome) will be measured with 4-meter ETDRS charts. Assessment at screening will include medical history, ophthalmic examination, confrontation visual field testing, visual acuity, reading speed, refraction, contrast sensitivity, assessment with x2.5 external telescope for distance and near vision, assessment for ocular dominance, binocular visual function, endothelial cell density, ocular coherence tomography (OCT) with volume scan, colour fundus photography, IVI, and EQ-5D-5L. Fundus fluorescein angiography (FFA) will be carried out in addition to OCT at baseline and only subsequently if clinically indicated as OCT cannot be performed post implantation of the device. The order of screening examinations will follow as per Figures 3 and 4, however, this may vary at site depending on the location of equipment. The detailed schedule is shown below in Table 2.

If all inclusion criteria are met at both screening visits, participants will be enrolled into the study. The required clinical information will be returned to the lead site (NICTU) and the study eye will be selected. The participant will be informed within 72 hours regarding which eye has been selected as the study eye and will be provided with a date to attend for Nd:YAG capsulotomy in the study eye, if not already done. After the participant has undergone the laser treatment, the Principal Investigator (PI) or designee will contact the CTU to determine group allocation. The participant will then be notified within 72 hours post laser treatment regarding group allocation.

Group 1 Care Pathway:

- Day 0: Surgery (surgical implantation of OriLens device)
- Day 1: Surgical review
- Day 7: Surgical review
- Assessments will be carried out at Months 1, 3, 6 and 12
- Low vision training at months 1, 3 and 12

Group 2 Care Pathway

- Day 0: No procedure

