10.3 Study Instruments

Best corrected distance visual acuity (BCDVA) will be obtained in both eyes by an optometrist trained in research studies using the ETDRS charts at screening visit one and months one, three, six and 12. Additionally, BCDVA will be obtained pre-operatively and on days one and seven post-operatively in the intervention group. BCDVA can be a variable endpoint depending on the assessor. In order to reduce variability, participants can be encouraged to read to achieve their best visual acuity. Furthermore, an additional independent assessor will repeat the BCDVA at the 12-month time point. Refraction will be prepared by the optometrist on the research team prior to the assessment and the independent assessor will be instructed not to look directly at the participant's eyes. As an additional measure to aid masking, the trial frames will be placed on the participant by the research optometrist.

Vision-related quality of life will be measured using the IVI (18). The IVI has been validated in AMD and the subscales of IVI (reading and assessing information, mobility and independence, and

emotional well-being) have been demonstrated to have superior-quality psychometric properties and validity (22, 23). It will be administered at baseline, and six and 12 months post-randomisation.

Health related quality of life will be measured using the EQ-5D-5L (17). The EQ-5D-5L is a generic preference-based instrument which provides a description of health using five dimensions (mobility, self-care, usual activities, pain/discomfort and anxiety/depression) each with five levels of severity. Responses are converted to an overall utility score which will be used for the calculation of quality adjusted life years (QALYs). Respondents are also asked to place their health on a visual analogue scale (VAS) where 0 represents the worst imaginable health state and 100 the best imaginable health state. It is recommended by NICE (24) for use in economic evaluations. It will be administered at baseline, and six and 12 months post-randomisation.

A resource use questionnaire has been developed specifically for the MIRROR study. It will measure participants' use of health services (community, social, hospital and care services) up to 12 months post-randomisation. It will also measure participants' use of privately purchased vision aids and the costs of these. It will be administered at six and 12 months post-randomisation.

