10.6.2 Statistical methods

The primary endpoint is the change from baseline of BCDVA at the 12-month time point in the study eye. The treatments will initially be compared using the independent t-test followed by a repeated measures analysis of covariance, adjusting for site, baseline BCDVA as a covariate and other covariates/factors where appropriate. Possible covariates/ factors will be discussed in the Statistical Analysis Plan (SAP) and may include size of scar, thickness of scar, and ocular dominance. Statistical diagnostic methods will be used to check for violations of the model assumptions and data transformations or non-parametric equivalents such as Mann-Whitney may be performed as appropriate. The primary data at 12 months are the BCDVA measurements by the independent assessor. The 12 month BCDVA data measured by the optometrist on the research team will be analysed as part of a sensitivity analysis.

The continuous secondary endpoints will be analysed in the same manner as the primary endpoint with an endpoint specific baseline covariate term included.

Analyses will be two-sided and tested at an a priori significance level of p=0.05. The primary time point has been defined as the 12-month time point. There is no adjustment for multiple testing at the different time points, as the primary outcome has been defined and prioritised.

For the mechanistic evaluation, descriptive statistics will be used to present the results. Also, the relationship between visual outcome and several factors (as discussed in Section 7.1) will be investigated using the independent t-test, 1-way analysis of variance, Pearson's correlation coefficient or non-parametric equivalents as appropriate depending on the scale of measurement of the factors.

Inter-rater reliability between the independent assessor and the optometrist on the research team will be tested for BCDVA at 12 months using the intra-class correlation coefficient.

Baseline characteristics, follow-up measurements and safety data will be described graphically and in tabular format using appropriate descriptive summary measures depending on the scale of measurement and distribution.

A detailed SAP will be written by the trial statistician prior to the final analysis.

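### At month 12 an unmasked scored acuity test always precedes the masked primary reading, so arm-specific prompting or effort can carry over; reversing the order is almost free

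*Protocol*

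**What the plan says.** Protocol section 8.4.1 sets the sequence at month 12. First, "BCDVA at the 12 month time point will initially be measured by the optometrist on the research team". Then, "An independent assessor will then repeat the BCDVA at the 12-month time point and this measurement will be used for the primary analysis". Sections 8.5 and 10.3 agree, describing the independent measurement as a duplicate or a repeat.

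Section 8.4.1 recognises that the endpoint depends on the tester: "BCDVA can be a variable endpoint depending on the assessor". Its response is "In order to reduce variability, participants can be encouraged to read to achieve their best visual acuity", and section 10.3 says the same. Neither section names the tester who may encourage or gives wording for it.

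Section 8.5 says of the routine testers, "As the presence of the device is obvious to the casual observer, it will not be possible to mask assessors", and of the participants, "Participants can also not be masked to the intervention". Section 9.4 repeats both points and offers the independent observer as the remedy.

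The listed masking safeguards are that the assessor does not look directly at the participant's eyes, that the optometrist refracts beforehand and fits the trial frame (8.4.1, 10.3), and that the assessor does not discuss the trial (9.4). Acuity procedure is otherwise left to the Trial Manual, which is not available here.

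Section 10.6.2 then uses the first reading: "The 12 month BCDVA data measured by the optometrist on the research team will be analysed as part of a sensitivity analysis". It also plans an intra-class correlation between the two testers.

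**The concern.** The independent assessor is the trial's one protection against assessor bias in the primary outcome. The safeguards control what that assessor sees and hears. None of them covers what the participant brings from a scored test taken beforehand with someone who knows the allocation.

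If the optometrist presses implanted participants harder than controls, even unintentionally, the letters found or the effort set in the first test may persist into the second. That would enter the primary difference as bias, and masking the second tester would not remove it.

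The route is avoidable. Masking needs the refraction and the frame placement to come first. The protocol gives no reason for the optometrist's scored test to come first as well.

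**Working it through.** **1. The protocol's own figure.** Inputs from section 8.6: difference 8.06 letters, SD 13.4, power 90%, and attrition printed as 10 and read here as 10%. Inputs from 10.6.2 and 9.1: two-sided 5%, 1:1 allocation.

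n per group = 2 × (1.960 + 1.282)² × 13.4² / 8.06² = 2 × 10.51 × 179.56 / 64.96 ≈ 58.1, rounded up to 59. With attrition, 59 / 0.90 = 65.6, rounded up to 66. Both match the protocol. Nothing in this point changes them.

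**2. What can and cannot bias the comparison.** Suppose the first test shifts the masked reading by c₁ letters on average in the implant arm and c₀ in the control arm. The bias in the difference is b = c₁ − c₀.

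- Chart memory, practice or fatigue that is equal in both arms gives c₁ = c₀ and b = 0. It would still sit in each arm's own change from baseline, because screening acuity is planned as a single optometrist reading.
- Encouragement or effort that depends on knowing the allocation gives c₁ ≠ c₀, so b is not zero.

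**3. Scale, by assumption.** The protocol gives no figure for carry-over. Suppose encouragement adds 2 to 4 letters more in the implant arm, and 25% to 50% of that persists:

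- lower end: 2 × 0.25 = 0.5 letters, and 0.5 / 8.06 = 6% of the planned difference
- upper end: 4 × 0.50 = 2 letters, and 2 / 8.06 = 25% of the planned difference

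These percentages only restate the assumption on the protocol's scale.

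**4. Effect on the test.** SE of the difference = 13.4 × √(2/59) = 2.467 letters. With no true effect and bias b, the two-sided rejection rate is

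1 − Φ(1.960 − b/SE) + Φ(−1.960 − b/SE).

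| b (letters) | b/SE | Rejection rate |
|---|---|---|
| 0 | 0 | 5.0% |
| 0.5 | 0.20 | 5.5% |
| 1 | 0.41 | 6.9% |
| 2 | 0.81 | 12.8% |

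**5. Order of steps.**

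| Step before the masked reading | Needed for masking? |
|---|---|
| Refraction by the optometrist | Yes: keeps the assessor from working close to the eye |
| Trial frame placed by the optometrist | Yes: same reason |
| Scored acuity test by the optometrist | No reason given |

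**The case against.** Several points on the other side have force.

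- **Chart memory.** A reader might infer that letters remembered from the first test distort the result. The protocol does not support that as a fault in the comparison. Both arms follow the same order, so a common effect largely cancels. The Trial Manual may also already specify alternate charts, an interval or a script.
- **Encouragement.** The sentence is general, precedes the mention of either month-12 tester in 8.4.1, and aims at lower variability. If the masked assessor also urges every participant to do their best, an earlier prompt has less room to matter. The text permits arm-specific encouragement; it does not show that it will occur.
- **Independence.** A reader might infer that the primary reading is not masked at all. That goes too far. The assessor-side safeguards are unaffected by test order, and only carry-over through the participant is at issue. The protocol also does not say that both tests fall on the same day, although the frame arrangement suggests it.
- **Intra-class correlation.** A reader might infer that reversal repairs the agreement analysis. It does not. Whichever test comes second can be anchored on the first.
- **Residual influence.** After reversal the same unmasked optometrist still refracts, optometrist acuity tests have taken place at months 1, 3 and 6, and the participant still knows the allocation.
- **Size.** The letter values are assumed, and all of them are below one standard error.

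What remains is narrow but sound: the order is fixed in the text, no listed safeguard covers carry-over through the participant, and the route can be closed cheaply.

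**Conclusion.** The point holds as an avoidable weakness in the measurement order, not as a demonstrated bias. The sequence, the unmasked first tester and the permitted encouragement are certain from the text. The size of any effect is not known. Under the stated assumption of 0.5 to 2 letters favouring one arm, with SD 13.4 and 59 per group, the false-positive rate of the 5% test would be about 5.5% to 12.8%. If carry-over is equal in both arms it stays at 5%.

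It would be wrong to conclude that the primary result is invalid, that the sample size needs to change, or that reversing the order would remove all influence of knowing the allocation.

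**What to change.** Amend sections 8.4.1 and 10.3 so that the month-12 sequence is:

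1. The research optometrist refracts and places the trial frame.
2. The masked assessor takes the first scored ETDRS reading, which is the primary value.
3. The research optometrist's scored reading follows and serves the sensitivity analysis in 10.6.2.

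Unless the Trial Manual already does so, require different chart versions for the two readings and the same instruction wording, including any encouragement, for both testers and both arms.

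The cost is a wording change in two sections and the manual. The staff and both measurements are already planned. The downside is that second-test fatigue moves to the sensitivity reading. The intra-class correlation should still be reported as agreement between two readings that are not independent.
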